protocol with the volunteer and document their consent to the research study. The physician and volunteer will then sign the study consent form.

4) Study procedures will begin after the study physician verifies that the participant meets inclusion/exclusion criteria, understands the medical risks of participation, and is capable of providing informed consent. [name], the senior study physician, will settle any disagreements among the study team as to a volunteer's eligibility, and will make the final decision as to study participation. Behavioral observations and testing will be carried out by one of the study clinicians. In the event of an emergency, one of the study physicians will be available by phone. [name] and other psychologists, nurses, and physicians are around the corner or down a corridor from the outpatient laboratory. We do not test research participants unless we are sure that a physician is available by telephone or by pager in the event of an emergency. A set of emergency procedures, including a list of physicians, telephone and pager numbers is posted in the outpatient laboratory.

Medication: Patients will be administered smoked marijuana at one of the following concentrations: High THC (5-10%)/Low CBD (<1%), Low THC (<1%)/High CBD (>10%), or placebo (0% THC and CBD). The order in which they receive each concentration will be randomized. Participants will complete 1 or 2 sessions per week depending on timing and subject availability. Because of cannabidiol's long terminal half-life (21-33 hours), we are allowing time for drug clearance in between sessions (at least 3 days) to avoid potential carryover effects (Consroe et al., 1991).

General Design: There will be three 4-hour laboratory sessions, which will occur between 0900 and 1300 hr, testing the effect of smoked marijuana on OCD symptoms. Sessions will occur once or twice per week over a period of approximately 3 weeks depending on each participant's availability.

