Laboratory Sessions: Participants will be instructed that they should not smoke either marijuana or cigarettes on the morning of a session (beginning at midnight). We will do a carbon monoxide (CO) test upon their arrival in the laboratory to verify nothing was recently smoked. Participants will also be given a breathalyzer test to ensure that they did not drink alcohol prior to arrival. At each visit, urine samples will be tested for drug use, and, for women of child-bearing age, for pregnancy. Subjects who are found to be pregnant will be discontinued from the study, but will receive payment for those procedures that they have already completed. Participants with high COs or those testing positive for drugs other than marijuana will be re-scheduled and possibly excluded from further participation. Patients will then receive either high THC (5-10%)/low CBD (<1%) marijuana, low THC (<1%)/high CBD (>10%) marijuana, or placebo (0% THC and CBD). The marijuana used in the study will be provided by the NIDA. We will guide participants through smoking individual puffs of marijuana using cue-dosing procedures until 50% of the cigarette has been smoked. Specifically, for each puff, participants will be instructed to inhale for 5 seconds and hold each puff in the lungs for 10 seconds. There will be approximately a 40-second interval between each puff. For the first hour after marijuana administration, clinical ratings, scales, and BP/HR will be obtained every 20 minutes. During the second hour, these measures will be repeated once every half-hour, and then again at the conclusion of the third hour (see Table 1). The session will end after the third hour. Participants will be allowed to leave the facility when they pass the field sobriety test, and will be instructed not to drive a car or use other drugs or alcohol for at least 8 hours after marijuana administration.

Table 1. Session Schedule

| TIME (min) | EVENT |
|------------|--|
| -50 | CO, collect urine, breathalyzer, start breakfast |
| -30 | Finish breakfast (set timer for 30 min), balance, TLFB, BP/HR, VAS, YBOCCS, STAI |
| 0 | Marijuana administration |
| 20 | BP/HR, VAS, YBOCCS, MRF, STAI |
| 40 | BP/HR, VAS, YBOCCS, MRF, STAI |
| 60 | BP/HR, VAS, YBOCCS, MRF, STAI |
| 90 | BP/HR, VAS, YBOCCS, MRF, STAI |
| 120 | BP/HR, VAS, YBOCCS, MRF, STAI |
| 180 | BP/HR, VAS, YBOCCS, MRF, STAI, Field Sobriety Test, participant discharge |

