There are also possible side effects following CBD administration. The medication has few psychoactive effects (e.g., Leweke et al., 2000; Fusar-Poli et al., 2009), although there is a report of decreased anxiety and increased sedation (400 mg; Crippa et al., 2004). One placebo-controlled study administered CBD (approximately 700 mg/day) to patients with Huntington's disease for 6 weeks and reported no significant adverse effect from the medication relative to placebo (Consroe et al., 1991). CBD doses up to 1500 mg/day have been given for several weeks to schizophrenic patients with no side effects reported (Zuardi et al., 1995, 2006).

Describe procedures for minimizing risks

All participants are fully informed of these effects, and because all currently smoke marijuana, these effects should be familiar to them.

The risks of marijuana and/or CBD exposure to a developing fetus or newborn are unknown, so women who participate in the study will be required to confirm that they are not pregnant or breastfeeding and are practicing an effective form of contraception (e.g. hormonal contraception or barrier methods) throughout the duration of the study.

In previous studies, participants have not found the study procedures to be stressful or difficult. They are monitored continuously throughout the experimental procedure. Emergency medical equipment is available in our laboratory, which is located in a hospital where a full medical emergency back-up team is constantly available. We anticipate that careful participant selection, dose selection and monitoring will obviate the need for such emergency care.

Methods to Protect Confidentiality

Describe methods to protect confidentiality

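### A low-cost safety addition: psychotic symptoms and suicide risk bar entry but are not scheduled to be asked about again before dosing at sessions 2 and 3

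*Combined protocol and SAP*

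**What the plan says.** **Entry.** Under Inclusion/Exclusion Criteria, exclusion 2 bars patients with psychotic symptoms. Exclusion 5 bars those with a Hamilton depression score above 25 or a clinical judgement of suicide risk. The methods listed are psychiatric evaluation and SCID, with the Hamilton scale added for exclusion 5. Consent Procedures and Study Procedures have a physician confirm whether major current psychopathology, suicide risk included, is present, and verify eligibility before study procedures begin.

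**Sessions.** There are three dosing sessions at least 3 days apart, over about 3 weeks. On the sequence of conditions, the plan states: "The order in which they receive each concentration will be randomized".

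**Before each dose.** Laboratory Sessions says: "At each visit, urine samples will be tested for drug use, and, for women of child-bearing age, for pregnancy". Each test has a consequence. For pregnancy: "Subjects who are found to be pregnant will be discontinued from the study". For other drugs, those "testing positive for drugs other than marijuana will be re-scheduled and possibly excluded from further participation". Table 1 puts CO, urine and breathalyzer at -50 minutes and, at -30 minutes, "Finish breakfast (set timer for 30 min), balance, TLFB, BP/HR, VAS, YBOCCS, STAI".

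**General safeguards.** Study Procedures states "Behavioral observations and testing will be carried out by one of the study clinicians" and "We do not test research participants unless we are sure that a physician is available by telephone or by pager". The section on minimizing risks adds: "They are monitored continuously throughout the experimental procedure".

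**The concern.** Both conditions can change within weeks, and both bear on whether a person should be given marijuana on a given day. By re-testing pregnancy and drug use at each visit, the plan accepts that some entry conditions need confirming again before a dose. It schedules nothing similar for these two.

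What is at stake is patient safety, not the analysis. A participant who developed suicidal thoughts or mild psychotic symptoms after screening could reach a later dose without being asked about them. High-THC marijuana is one of the three conditions and may fall at session 2 or 3. The plan's own background reports that drug users whose hair tested positive for THC alone had more schizophrenia-like symptoms than two comparison groups. That is a cross-sectional association and does not show acute harm, but it is a reason to ask.

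**Working it through.** The plan gives no figure to reproduce on this point, so the check compares sections and then works out time.

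**1. What is scheduled at each session.**

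| Condition | At screening | Before each session | Stated consequence in a session |
|---|---|---|---|
| Pregnancy | yes | yes | discontinue |
| Other drug use | yes | yes | re-schedule, possibly exclude |
| Psychotic symptoms | yes | not scheduled | none specific |
| Suicide risk | yes | not scheduled | none specific |

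**2. Pre-dose measures in Table 1.** At -50 minutes: CO, urine, breathalyzer (3). At -30 minutes: balance, TLFB, BP/HR, VAS, YBOCCS, STAI (6). Total 3 + 6 = 9. Assessment Instruments describes the VAS as covering physical symptoms, mood, anxiety and OCD symptoms; the STAI is an anxiety scale and the YBOCCS an OCD scale. None of the nine is described as covering psychosis or suicidality. The individual VAS items are not reproduced, so the finding is that none is described, not that none exists. The SCID, Hamilton depression scale and psychiatric examination are listed as instruments but do not appear in Table 1.

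**3. Triggers tied to measurements.** Safety Measures calls a physician on blood pressure or heart rate. Criteria for Early Discontinuation names OCD deterioration as its one specific psychiatric ground. It also has a ground for serious or intolerable adverse events and an open-ended one for other conditions. No dosing hold is tied to a mood or anxiety score.

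**4. Elapsed time.** Session 1 to session 3 is two gaps of at least 3 days: 2 × 3 = at least 6 days. The interval from screening to session 1 is not stated.

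**5. Room in the schedule.** Durations from Assessment Instruments for the -30 minute block: TLFB 3 + BP/HR 1 + VAS 2 + YBOCCS 1 to 2 + STAI 3 = 10 to 11 minutes. That leaves 30 - 11 = 19 to 30 - 10 = 20 minutes, less the balance test, which has no stated duration.

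**6. Staff time,** assuming 2 to 5 minutes per check.
- Sessions 2 and 3, 15 completers: 15 × 2 = 30 checks; 30 × 2 = 60 to 30 × 5 = 150 minutes, or 1 to 2.5 hours.
- With session 1 as well: 15 × 3 = 45 checks; 90 to 225 minutes, or 1.5 to 3.75 hours.

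These counts measure workload only. They say nothing about how often either condition would be found.

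**The case against.** The strongest reply is that this is an optional refinement in a sample already screened to lower the risk. The plan excludes anyone with a first-degree relative who has schizophrenia, a lifetime history of schizophrenia, bipolar disorder or substance-induced psychosis, or depression needing medical intervention. Participants must have used marijuana before without intolerable effects. Only half a cigarette is smoked per session. Table 1 gives at least 50 minutes of contact before each dose, with mood and anxiety ratings. Psychologists, nurses and physicians are close by, and study doctors have wide discretion to stop. Pregnancy and drug screens are simple urine tests, so repeating them does not imply that interview criteria must be repeated.

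Most of this stands and is why the gain is modest. It does not close the gap. Screening describes the participant at entry. Ratings and observation may show marked distress, but suicidal thoughts or mild symptoms can go unnoticed unless someone asks. The sample is not clearly low risk either: exclusion 5 allows Hamilton scores up to 25, and the Data Analytic Plan gives major depression as an example of a comorbid diagnosis to explore as a covariate.

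Three stronger readings are tempting but unsupported:
- **That the plan contradicts itself.** Other clinical entry bars, such as a current eating disorder, are not re-checked either, and no rule requires every criterion to be confirmed before each dose. Singling out these two is a judgement about acute states.
- **That participants are left unprotected, or that doctors lack authority to stop.** The safeguards above say otherwise.
- **That study marijuana is shown to cause psychosis or suicidality here.** The documents give no event rate and no link to suicidality. The continuation report records no serious adverse event, though with five enrolled that is little reassurance.

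**Conclusion.** The point holds as a cheap improvement in patient safety, worth considering. It is not an error or an inconsistency, and it does not touch the endpoints, sample size or analysis model. As written, the schedule does not ask about either condition before a later dose.

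The benefit cannot be quantified, because the documents give no rate for either event between sessions. The conclusion rests on two assumptions: that the unseen VAS items do not already ask about psychosis or suicidal thoughts, and that clinicians have no unwritten practice of asking. If either is wrong, the remedy reduces to writing down what is already done and what follows a positive answer.

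**What to change.** At the -50 or -30 minute step of sessions 2 and 3, have the study clinician already present ask briefly about current psychotic symptoms and suicidal thoughts. Do the same at session 1 if it is not on the day eligibility was verified. If either is present, withhold the dose and call the study physician, who decides between re-scheduling and discontinuation. Record the answer and the decision. Naming both conditions under Criteria for Early Discontinuation would be clearer but would add no new authority.

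The cost is the 1 to 2.5 clinician hours worked out above (up to 3.75 if session 1 is always included), plus physician time after a positive answer, which cannot be estimated from the documents. The question is a prompt to act and does not replace the screening evaluation. The main downside is an occasional postponed or lost session, which matters with 15 completers each needed under all three conditions. Re-scheduling is already part of the plan for a high CO reading or a positive drug screen.

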Background, Significance and Rationale

Background, Significance and Rationale

Previous research has suggested that the endocannabinoid system may serve a regulatory function in frontal-striatal brain circuits which have been implicated in anxiety disorders and Obsessive Compulsive Disorder (OCD) (Lutz et al. 2015, Gremel et al. 2016). In addition, there is an emerging body of evidence which demonstrates a potential role for drugs that target cannabinoid receptors in the treatment of anxiety disorders and Tourette's syndrome (Curtis et al. 2009, Müller-Vahl et al. 2013, Blessing et al. 2015). Data from animal studies (Deiana et al. 2011, Nardo et al. 2013, Breuer et al. 2016) suggest a potential benefit to these compounds in OCD as well. However, to date studies in humans are limited to case reports (Schindler et al. 2008). The purpose of this double-blind, placebo-controlled, within-subject study is to examine the effects of different cannabinoids, delivered in a laboratory setting, on adults with primary OCD. In order to accomplish this, adults with OCD who are also occasional marijuana smokers will be recruited for 3 outpatient laboratory sessions over the course of 2-3 weeks. In the laboratory, patients will receive different combinations of the cannabinoids tetrahydrocannabinol (THC, the active ingredient in the marijuana plant) and cannabidiol (CBD, a cannabinoid constituent of marijuana which has demonstrated therapeutic potential across a variety of psychiatric disorders including depression, anxiety, and psychosis [Campos et al. 2012]) or placebo. We will then measure whether or not patients respond to these agents (i.e. experience a significant reduction in their OCD symptoms) in the acute setting.

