** BP/HR = blood pressure and heart rate; VAS = Visual Analogue Scale; YBOCCS = Yale-Brown Obsessive-Compulsive Challenge Scale; MRF = Marijuana Rating Form; STAI = State/Trait Anxiety Inventory; TLFB = Marijuana Timeline Followback

Patients will be required to take public transportation to and from the laboratory each session, for which they will be reimbursed. Study clinicians will conduct the Field Sobriety Test. After confirming that the participant has passed the Field Sobriety Test, the patient will be allowed to leave the laboratory. If a participant is still impaired at the end of the session, she or he will be asked to remain in the laboratory until the effects wear off, and will be paid extra (i.e. \$10 per hour for any additional time in the laboratory). In the event that the impairment does not resolve in a timely manner, a study physician will determine whether the person can leave the laboratory or if further action is needed. It is worth noting that in our experience, it is exceedingly rare (<1% of all participants) for marijuana smokers to remain intoxicated several hours after smoking marijuana in the laboratory.

Laboratory Facility: Experimental sessions will be conducted in the Substance Use Research Center (SURC) located on the 3rd floor of the NYS Psychiatric Institute.

Safety Measures: Vital signs (heart rate and blood pressure) will be monitored in each session. If SBP > 180 mmHg, DP > 110 mmHg, or HR > 120 bpm, these measures will be taken 2 additional times at 2 min intervals: A physician will see the participant immediately if blood pressure or heart rate remain above these levels for 3 continuous readings.

Data Analysis: A between and within-subject repeated measures analysis of variance (ANOVA) with planned comparisons will be implemented to determine the effects of marijuana on OCD symptoms

You can upload charts or diagrams if any

Criteria for Early Discontinuation

Criteria for Early Discontinuation

Participants are free to withdraw from the study at any time for any reason. Study doctors are to discontinue patients from the study if patients:

- Request an early discontinuation or withdraw consent.
- Experience a serious or intolerable adverse event that prevents the patient from continuing.

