Cannabis Effects: We will use a random-effects linear mixed model to evaluate changes in each continuous outcome (YBOCCS, OCD-VAS, STAI-S MRF, cardiovascular measures) as a function of condition (THC, CBD, placebo), time point, and their interaction. Mixed-effects modeling accounts for clustering of repeated measures within subjects, allows time to be modeled as a continuous rather than categorically, and has been used in similar acute pharmacological challenge studies (Rodriguez et al. 2013). The model will include participants as a random effect, condition and time as fixed within-subjects factors, the interaction between condition and time, and a random intercept. Given that the interval between sessions increases over the course of each session, we will model time as a continuous variable. We will use contrasts within each mixed-effects linear regression model to estimate differences in outcomes between both active cannabis varieties and placebo at different time points. All statistical tests will be conducted using an alpha level of 0.05, two-tailed.

Other Effects: Though we have no a priori hypotheses about the effects of age, gender, comorbid diagnoses (e.g. MDD), or other factors that might influence our participants' response to cannabis, we will nonetheless explore the possibility of such effects by including these factors as covariates in separate analyses.

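### The protocol text names a repeated measures ANOVA and the Data Analytic Plan a random-intercept mixed model for the same question, with no rule on which governs and no between-subject factor defined

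*Combined protocol and SAP*

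**What the plan says.** Under Study Procedures, the Data Analysis paragraph is one sentence: "A between and within-subject repeated measures analysis of variance (ANOVA) with planned comparisons" is to be used to determine marijuana's effect on OCD symptoms. It gives no error term, degrees of freedom, coding of time or rule for missing sessions.

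The Data Analytic Plan, under Cannabis Effects, says: "We will use a random-effects linear mixed model to evaluate changes in each continuous outcome". The outcomes listed there include the YBOCCS and the OCD visual analogue scale. On structure it says "The model will include participants as a random effect, condition and time as fixed within-subjects factors", then "the interaction between condition and time, and a random intercept". On time it says "we will model time as a continuous variable". Contrasts are used "to estimate differences in outcomes between both active cannabis varieties and placebo at different time points", at a two-sided 0.05 level.

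The Background section describes a "double-blind, placebo-controlled, within-subject study". Each participant receives all three varieties in randomised order, in separate sessions.

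**The concern.** Both statements are current, both are commitments, and both address the effect of cannabis on OCD symptoms. Neither is labelled primary, supportive or superseded. Neither is struck through, although the document marks other deletions that way.

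The ANOVA sentence also promises a between-subject component. Condition and time are both within-subject, and no grouping factor is named in either place. Order of administration could have been one, but neither analysis mentions it. Age, gender and comorbidity appear only as exploratory covariates in separate models.

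Two things are at stake. With two pre-stated analyses and no precedence, the choice between them can be made after the results are seen. And the choice can matter, because the two analyses usually measure the condition effect against different variation.

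**Working it through.** The documents state no power, effect size, SD or standard error, so there is no figure of theirs to reproduce. The check asks how far apart the two analyses can be on the same data.

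**Inputs from the documents.** 15 completers (Description of Subject Population); 3 conditions; 6 post-dose readings at 20, 40, 60, 90, 120 and 180 minutes (Table 1); a participant intercept as the only random effect (Data Analytic Plan).

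**Assumptions.** Complete data. The ANOVA uses its conventional error term. The variance left after removing the participant effect is scaled to 1, of which a share ρ is common to all readings in a session. ρ is then the within-session correlation, taken as 0.1, 0.3 and 0.5. The contrast is one active variety minus placebo, averaged over the 6 post-dose readings.

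**ANOVA.** Condition is tested against participant-by-condition variation, with 14 × 2 = 28 df:

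SE² = 2[(1 − ρ) + 6ρ]/(15 × 6) = 2(1 + 5ρ)/90.

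**Mixed model as written.** There are 15 × 3 × 6 = 270 readings. Six fixed coefficients and 14 participant contrasts leave 250 residual df. The session variance falls into that pooled residual, carried by only 28 of the 250 df:

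expected residual = (1 − ρ) + (28 × 6/250)ρ = 1 − 0.328ρ, so SE² = 2(1 − 0.328ρ)/90.

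**Ratio of standard errors** = √[(1 + 5ρ)/(1 − 0.328ρ)]. The mixed model's type I error is approximately 2[1 − Φ(1.97/ratio)].

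| ρ | (1 + 5ρ)/(1 − 0.328ρ) | SE ratio | 1.97/ratio | Type I error, mixed model |
|---|---|---|---|---|
| 0 | 1.000/1.000 | 1.00 | 1.97 | 0.05 |
| 0.1 | 1.500/0.967 | 1.25 | 1.58 | 0.11 |
| 0.3 | 2.500/0.902 | 1.67 | 1.18 | 0.24 |
| 0.5 | 3.500/0.836 | 2.05 | 0.96 | 0.34 |

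Simulating 20,000 null trials at each ρ gave mixed-model type I errors of 0.114, 0.240 and 0.336 for ρ = 0.1, 0.3 and 0.5. The ANOVA stayed at 0.049 to 0.050.

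**How often the conclusions differ.** A separate simulation used all 7 Table 1 readings, an assumed residual SD of 1.5 and a session SD of 1.0, so ρ = 1/(1 + 2.25) = 0.31. The point estimates were identical when the mixed model was evaluated at the mean assessment time. The standard errors were 0.420 (ANOVA) and 0.236 (mixed model), a ratio of 1.78. With an assumed true effect of −0.8, the two disagreed at 0.05 in 33% of 500 datasets, always with only the mixed model significant. With a session SD of 0 they disagreed in 1.4%.

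**Other contrasts.** For the linear condition-by-time slope the direction reverses. The ANOVA error contains no session variance, so the ratio is √[(1 − ρ)/(1 − 0.328ρ)] = 0.96, 0.88 and 0.77 at the three values of ρ. For a paired comparison at one time point against the fitted line, the ratio runs from about 1.2 to 2.7 depending on the time. Part of that gap comes from the straight line borrowing from other readings, not from the error term.

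**The case against.** The strongest reply is that the numerical gap comes entirely from the missing session term in the mixed model. Add a participant-by-session effect and the model reproduces the ANOVA condition test in complete, balanced data; with no session variance the two already agree on average. That is correct. It is why the two edits belong together, and why the figures measure what the choice can cost rather than a general property of ANOVA against mixed models.

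It is also fair that 28 df, categorical time and deletion of incomplete participants are ANOVA conventions that the protocol sentence does not state, and that the plan gives no degrees-of-freedom method for its model. The averaged post-dose contrast is not one the plan names. The Data Analytic Plan is more detailed and justifies its choice, so it is probably the intended analysis, but nothing in the document says so.

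Three stronger readings are tempting and not supported:

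- A reader might infer that the ANOVA would throw away a quarter of the data, from 15 completers out of 20 enrolled, or lose paid-for sessions, since 2 of the first 5 participants discontinued. No part of the document says that those who left completed any session. If they did not, the mixed model has no outcome data from them either.
- A reader might infer that the protocol asserts a between-subject treatment factor. It does not; the word is undefined, and could have meant order or a covariate.
- A reader might infer two rival primary analyses. Neither is ranked, and the absence of ranking is the defect.

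**Conclusion.** The point stands as a contradiction in current text: two analyses for one question, no precedence, and a between-subject component with no factor behind it. That much needs no assumption.

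The numerical consequence is conditional. It applies to the mean post-dose condition contrast, with 15 completers, complete data, the conventional ANOVA error term and a within-session correlation of 0.1 to 0.5. There the ANOVA standard error is roughly 1.2 to 2.0 times the mixed-model one, and the mixed model as written rejects a true null about 11% to 34% of the time instead of 5%. With no session-level variance the difference disappears on average; slope and single-time contrasts have other ratios. Some session-level variation is plausible, since symptoms can differ from day to day, but the documents give nothing from which to estimate it.

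This should be corrected. The progress summary reports enrolment ongoing with 2 completers, so at that stage it could be settled before results were known.

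**What to change.** Make these changes in one edit:

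1. Replace the ANOVA sentence under Study Procedures with a cross-reference to the Data Analytic Plan as the single governing analysis, and remove the word between.
2. In the Data Analytic Plan, add a participant-by-session random effect to the participant intercept. With one session per condition, this is the same as participant-by-condition.
3. State that all randomised participants with data from at least one session are included.

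Do not make the first change without the second: the ANOVA is the one of the two that held its error rate for the condition contrast.

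The cost is a few sentences and no change to data collection. The downside is wider, but valid, standard errors for the condition contrasts.
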